8.5 Impact of COVID-19

Additional sensitivity analyses as a result of the global COVID-19 pandemic are not anticipated as the onset of the pandemic was subsequent to all subjects completing Week 48 and therefore there is no impact on the analysis of the secondary efficacy endpoint.

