10.2.2 Exposure-adjusted incidence rate and exposure-adjusted event rate

The time at risk (in days) at AE onset is the same as the time since first bimekizumab dose as described in [Section 10.2.1](#).

Total time at risk (as defined in [Section 10.1](#)) and time at risk at AE onset will be divided by 365.25 to give years at risk.

EAIR and EAER will be calculated separately for tables including all events in AS0008 and AS0009 combined, and for tables including events with onset in AS0009 only. The former tables will use time at risk relative to the start date of bimekizumab 160mg or 320mg (for the ‘BKZ 160mg’ and ‘BKZ 320mg’ columns) and time at risk relative to the date of the first dose of bimekizumab (for the ‘BKZ Total’ column). The latter table will use time at risk relative to the start date of study medication in AS0009.

The EAIR is defined as the number of subjects with a specific AE adjusted for the exposure and will be scaled to 100 patient-years:

$$\frac{EAIR = 100 * n_{AE}}{\sum_{i=1}^{n_{AE}} T_{Exp,i} + \sum_{j=1}^{n_{noAE}} T_{Risk,j}} \quad (20)$$

Where n_{AE} is the number of subjects with the AE, $T_{Exp,i}$ is a subject’s time at risk at AE onset in years (equation [15] in years) and $T_{Risk,j}$ is the time at risk in years for subjects who did not experience the AE of interest.

If a subject has multiple events at the level of coding evaluated, the time at risk at AE onset is calculated to the first occurrence of the AE.

Exact Poisson 95% CIs for incidence rates are calculated using the relationship between the Poisson and the chi-square distribution (Ulm, 1990; Fay and Feuer, 1997):

$$LCL = \frac{\chi^2_{2n,\frac{\alpha}{2}}}{2} \quad (21)$$

$$UCL = \frac{\chi^2_{2(n+1),1-\frac{\alpha}{2}}}{2} \quad (22)$$

$$CI_{Lower} = 100 * \frac{LCL}{\sum_{i=1}^{n_{AE}} T_{Exp,i} + \sum_{j=1}^{n_{noAE}} T_{Risk,j}} \quad (23)$$

$$CI_{Upper} = 100 * UCL \frac{UCL}{\sum_{i=1}^{n_{AE}} T_{Exp,i} + \sum_{j=1}^{n_{noAE}} T_{Risk,j}} \quad (24)$$

where n_{AE} is the number of subjects with the AE and is the basis for the number of the degrees of freedom for the chi-square quantile for the upper tail probability χ^2 , $T_{Exp,i}$ is a subject's time at risk at AE onset in years, n_{noAE} the number of subjects without the specific AE and $T_{Risk,j}$ the total time at risk for subjects who did not experience the AE.

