10.2.4 Impact of COVID-19

In order to assess the impact of the COVID-19 global pandemic on the primary safety endpoint of incidence of TEAEs and serious TEAEs, additional listings and summaries will be presented.

For reporting purposes AEs will be assigned to ‘Prior to COVID-19 pandemic’, ‘During the COVID-19 pandemic’ or ‘Post the COVID-19 pandemic’ based on the following:

- If the date of AE onset (based on imputed start date) is prior to 11 March 2020 the AE will be assigned as ‘Prior to COVID-19 pandemic’
- If the date of AE onset (based on imputed start date) is on or after 11 March 2020 the AE will be assigned as ‘During the COVID-19 pandemic’
 - The date of 11 March 2020 is chosen as the date the World Health Organization declared COVID-19 as a pandemic.

- If the date of AE onset (based on imputed start date) is after the date on which the World Health Organization declares the end of the COVID-19 pandemic the AE will be assigned as ‘Post the COVID-19 pandemic’
 - If the date of the end of the COVID-19 pandemic is on or after the date of last subject, last visit, the ‘Post the COVID-19 pandemic’ phase will not apply.

The following categories of TEAE will be summarized by MedDRA SOC, HLT and PT, including EAIR and EAER:

- All TEAEs by time of onset relative to COVID-19 pandemic (‘Prior to COVID-19 pandemic’, ‘During the COVID-19 pandemic’ and ‘Post the COVID-19 pandemic’)
- All serious TEAEs by time of onset relative to COVID-19 pandemic (‘Prior to COVID-19 pandemic’, ‘During the COVID-19 pandemic’ and ‘Post the COVID-19 pandemic’)
- All COVID-19 related TEAEs by treatment at completion of AS0008 and overall
 - COVID-19 related TEAEs will be identified based on the verbatim term including the text string ‘COVID’. These will include confirmed or suspected COVID-19 infections.

TEAEs leading to study discontinuation and/or permanent withdrawal of study medication will be summarized by MedDRA SOC, HLT, and PT, and by time of onset relative to COVID-19 pandemic (‘Prior to COVID-19 pandemic’, ‘During the COVID-19 pandemic’ and ‘Post the COVID-19 pandemic’).

A separate listing of all COVID-19 related AEs will be presented, where COVID-related AEs are identified as described above. In addition, the time of onset of each AE relative to the COVID-19 pandemic will be flagged in all AE listings.

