For all listings and summaries described above the ‘Post the COVID-19 pandemic’ phase will be omitted if the date of the end of the COVID-19 pandemic is on or after the date of last subject, last visit.

For the purpose of calculating EAIR and EAER prior to, during, and post the COVID-19 pandemic the rules in [Table 10-5](#) will be applied in the calculation of exposure time at risk. An individual subject may therefore be counted in the denominator for all applicable periods (‘Prior to COVID-19 pandemic’, ‘During the COVID-19 pandemic’ and ‘Post the COVID-19 pandemic’), dependent on whether the subject is still considered at risk at the time of the start date for each successive period. The time at risk will be calculated separately for each period in which the subject is counted. Subjects who are no longer in the exposure time at risk period ([Table 10-2](#)) on the start date of a specific COVID-19 reporting period will not be counted in the denominator for that period ie, a subject who has withdrawn from the study prior to 11 March 2020 and is no longer at risk will not be included in the denominator for the ‘During the COVID-19 pandemic’ or the ‘Post the COVID-19’ pandemic periods.

Table 10-5: Calculation of exposure time at risk in relation to COVID-19

Study Period	Start Date	End Date	Duration of Exposure

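### The exposure-adjusted rates planned for COVID-19 related TEAEs are diluted by pre-pandemic time at risk and cannot be read as COVID-19 incidence during the pandemic

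*SAP*

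**What the plan says.** SAP 10.2.4 opens its list of tables with "The following categories of TEAE will be summarized by MedDRA SOC, HLT and PT, including EAIR and EAER". Two of the three entries, all TEAEs and all serious TEAEs, are split by onset before, during or after the pandemic. The third is "All COVID-19 related TEAEs by treatment at completion of AS0008 and overall"; it has treatment-group columns and no period columns.

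The same section introduces Table 10-5 with "For the purpose of calculating EAIR and EAER prior to, during, and post the COVID-19 pandemic the rules in", followed by the table reference. Table 10-5 cuts each subject's time at risk at 11 March 2020 and at the end of the pandemic. The accompanying text drops from a period any subject no longer at risk when it starts. On the cut date the SAP says: "The date of 11 March 2020 is chosen as the date the World Health Organization declared COVID-19 as a pandemic".

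SAP 10.2.2 sets the general rule for EAIR and EAER. For tables limited to events with onset in AS0009 it states: "The latter table will use time at risk relative to the start date of study medication in AS0009". It also equates time at risk at AE onset with time since first bimekizumab dose.

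SAP 8.5 records that "the onset of the pandemic was subsequent to all subjects completing Week 48".

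On case finding, SAP 10.2.4 says "COVID-19 related TEAEs will be identified based on the verbatim term including the text string" COVID, and adds: "These will include confirmed or suspected COVID-19 infections". SAP 12.5 describes a separate eCRF page for visits affected by COVID-19, on which confirmed or suspected infection is one of the recorded relationships. The SAP does not link that page to the AE search.

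**The concern.** A rate of COVID-19 events is informative only over time in which COVID-19 could occur. The SAP accepts this for its period-split tables, but the one table devoted to COVID-19 events does not get the same treatment. Read as written, both the person-time of subjects without an event and the time to onset of subjects with one begin at the first AS0009 dose, well before the pandemic.

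At stake is the only pooled COVID-19 rate in the plan, and the only one by treatment group. Infections (serious, opportunistic, fungal and TB) are a pre-specified safety topic in Protocol 9.1.3. A reader of the study report would naturally take a figure per 100 subject-years of COVID-19 related events as incidence on drug during the pandemic, and that figure would be too low.

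**Working it through.** The documents give no rate for this table, so there is no planned figure to reproduce. The check is on person-time.

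**Inputs**
- Maximum duration per subject: 204 weeks of treatment plus 20 weeks to the SFU Visit = 224 weeks, matching SAP Section 2.
- Time at risk for a full completer under SAP Table 10-2: 204 × 7 + 140 + 1 = 1569 days, or 224.1 weeks.
- Pre-pandemic time P: at least 48 weeks (336 days) for anyone who reached Week 48, from SAP 8.5. The documents do not give the actual distribution. I take 96 weeks (672 days) as an assumed middle value. As a ceiling I use 15 May 2017 (the final protocol date in SAP Section 1) to 11 March 2020, which is 1031 days or 147.3 weeks.

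**Which denominator applies**
The table is not split by period, so the sentence introducing Table 10-5 does not reach it. It is a table of AS0009-onset events, so 10.2.2 does.

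**Share of time that is pre-pandemic**
48 / 224 = 21%.

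**Dilution of the EAER when all subjects complete**
With the same events in the numerator, pandemic-time EAER / whole-study EAER = T / (T − P), where T = 1569 days.

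| P | Calculation | Factor |
|---|---|---|
| 48 weeks | 1569 / (1569 − 336) = 1569 / 1233 | 1.27 |
| 96 weeks (assumed) | 1569 / (1569 − 672) = 1569 / 897 | 1.75 |
| 147.3 weeks (ceiling only) | 1569 / (1569 − 1031) = 1569 / 538 | 2.92 |

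**Illustration**
Take 285 completers (the planned maximum) and an assumed 30 events; the event count cancels from the ratio.
- Whole-study time: 285 × 1569 / 365.25 = 1224.3 subject-years, EAER 2.45 per 100.
- Pandemic time with 48 weeks before: 285 × 1233 / 365.25 = 962.1 subject-years, EAER 3.12.
- Pandemic time with 96 weeks before: 285 × 897 / 365.25 = 699.9 subject-years, EAER 4.29.

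**Earlier withdrawals**
Assume 20% of the 285 (57 subjects) leave before the pandemic, each contributing on average half of P, and 228 complete.
- P = 48 weeks: (57 × 24 + 228 × 224.14) / (228 × 176.14) = 1.31.
- P = 96 weeks: (57 × 48 + 228 × 224.14) / (228 × 128.14) = 1.84.

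**EAIR**
The factors above are exact for the EAER only. In the EAIR a subject with an event stops contributing at onset. That shortens the pandemic part of that subject's time and leaves P unchanged, so the EAIR is diluted at least as much.

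**Numerator**
No figure can be computed, because the documents give neither verbatim terms nor a capture rate. If the string found a share s of true cases and nothing else, the rate would scale by s.

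**The case against.** The strongest reply has four parts.

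1. *The denominator is inferred.* The SAP names none for this table, and Table 10-5 sits in the same section, so the sponsor may have meant to use it. That is possible, but the sentence introducing Table 10-5 limits its scope, and a programmer following the text would apply 10.2.2. The silence itself needs correcting.

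2. *The rate is legitimate.* Events over all AS0009 exposure is a properly defined rate, built like the other AS0009-only TEAE rates, and the numerator is not restricted to onset on or after 11 March 2020. This stands. A reader might infer that the rate is simply wrong; it is not. It answers a different question from the one its title suggests.

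3. *Pandemic-period rates are already planned.* All TEAEs and serious TEAEs are shown by period down to PT, and onset period is flagged in the AE listings. This helps, but those tables neither pool COVID-19 related events nor split them by treatment group. COVID-19 events are selected by verbatim text rather than by PT, so nothing ensures that particular PT rows isolate them.

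4. *Low consequence.* The table is descriptive, no external comparison is planned, and SAP 4.3 leaves COVID-19 tables out of the Week 108 interim. This limits the importance of the point but does not remove it.

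A reader might also infer that the text search makes the numerator wrong. The documents do not show that. Terms without the string could be missed, and terms that mention COVID without an infection could be caught. However, the SAP says the matches will include infections, not that all are infections. Matched events are listed individually and tabulated by PT, so false matches would be visible; missed synonyms would not be. This is a risk of unknown size.

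**Conclusion.** The point holds for the denominator. Followed as written, the SAP gives a COVID-19 related TEAE rate that is valid per AS0009 exposure but lower than the pandemic-period rate. For full completers the EAER is lower by a factor of about 1.27 at 48 pre-pandemic weeks and about 1.75 at 96 weeks. The first rests on SAP 8.5 and complete follow-up; the second adds an assumed calendar position. Withdrawals before the pandemic increase both.

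Two stronger readings are not supported. One is that every subject contributes at least 48 pre-pandemic weeks. That holds only for those who reached Week 48; earlier leavers contribute less, all of it pre-pandemic if their risk window closed before 11 March 2020. The other is that the rate is cut to about a third. The 2.92 ceiling supposes that every subject received a first AS0009 dose on the date of the final protocol, which the documents do not suggest.

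The case-finding rule is a secondary matter: a possible misclassification, not a demonstrated error.

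**What to change.** **Denominator.** State in SAP 10.2.4 that for this table:
- the subjects are those still at risk on 11 March 2020;
- time at risk is the Table 10-5 During time plus any Post time;
- time to onset in the EAIR is counted from 11 March 2020. This must be written out, because 10.2.2 otherwise counts it from first dose;
- any COVID-19 related event with earlier onset is listed separately and left out of the rate, since it would have negative time to onset.

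**Numerator safeguard.** Replace the single string with a case-insensitive synonym list, for example COVID, SARS-COV and CORONAVIRUS. Have matched terms medically reviewed before database lock, and cross-check them against confirmed or suspected infections on the Section 12.5 eCRF page. SAP 12.3 already uses study-physician review of individual terms for opportunistic infections, so the process exists.

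**Cost.** SAP wording, one extra denominator variable built from durations that Table 10-5 already derives, and a short term review. No new data are needed.

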10.3 Clinical laboratory evaluations

The routine clinical laboratory evaluations specified in [Table 10–6](#) will be summarized. If any additional analytes are also recorded they will be listed only.

Table 10–6: Laboratory measurements

Hematology	Biochemistry	Urinalysis
Basophils	Calcium	Urine dipstick for pregnancy testing ^a
Eosinophils	Chloride	Urinalysis ^b
Lymphocytes	Magnesium	
Atypical lymphocytes	Potassium	
Monocytes	Sodium	
Neutrophils	Glucose (random)	
Hematocrit	BUN	
Hemoglobin	Creatinine	
MCH	AST	
MCHC	ALT	
MCV	ALP	
Platelet count	GGT	
RBC count	Total bilirubin	
WBC count	LDH	
	Total cholesterol	
	Uric acid	
	CRP	

ALP=alkaline phosphatase; ALT=alanine aminotransferase; AST=aspartate aminotransferase; BUN=blood urea nitrogen; CRP=high sensitivity C-reactive protein; GGT=gamma glutamyltransferase; LDH=lactate dehydrogenase; MCH=mean corpuscular hemoglobin; MCHC=mean corpuscular hemoglobin concentration; MCV=mean corpuscular volume

^a A urine pregnancy test will be performed for women of childbearing potential if there is a suspicion of pregnancy. A positive urine pregnancy test should always be confirmed with a serum pregnancy test.

^b These measurements will be performed only if a urinalysis is required for safety reasons.

Separate summary tables for hematology and biochemistry variables will be provided, based on central laboratory data only, from scheduled visits (including the SFU visit). Observed values and changes from AS0009 Laboratory Baseline will be summarized, by treatment group at completion of AS0008 and overall. CRP will be summarized separately as described in [Section 8](#).

In the case where laboratory values (with the exception of CRP) are below the LLOQ, then these will be set to the midpoint between 0 and the LLOQ for the purpose of summarizing the data and calculating changes from Baseline. The original value will be reported in any listings.

Summary tables of the number and percentage of subjects experiencing at least 1 on-treatment markedly abnormal value during the Treatment Period (including unscheduled and repeat assessments, but excluding any measurements that occurred prior to the first administration of study medication in AS0009 or more than 140 days after the last administration of study medication) for each hematology and biochemistry variable will be presented by treatment group at completion of AS0008 and overall. Markedly abnormal values for hematology and biochemistry are defined in [Table 10-7](#) and [Table 10-8](#).

Tables of markedly abnormal laboratory data subject numbers will be provided including all values classified as markedly abnormal at scheduled and unscheduled visits. For all outputs presenting markedly abnormal laboratory values, only central laboratory data will be included.

Table 10-7: Definitions of markedly abnormal hematology values

Variable (SI Units)	Markedly Abnormal Definition	
	Low	High
Hemoglobin (g/L)	<80	>40 above ULN
Lymphocytes ($10^9/L$)	<0.5	>20.0
Neutrophils ($10^9/L$)	<1.0 ^a	N/A
Platelets ($10^9/L$)	<50	N/A
Leukocytes ($10^9/L$)	<2.0	>100

N/A=not applicable; ULN=upper limit of normal

Data source: modified from Appendix Rheumatology Common Toxicity Criteria v.2.0 presented in Woodworth et al, 2007

^a Withdrawal criteria for neutrophils is <0.5

Table 10-8: Definitions of markedly abnormal biochemistry values

Variable (SI Units)	Markedly Abnormal Definition	
	Low	High
ALP	N/A	>5.0 x ULN
ALT	N/A	>5.0 x ULN

Table 10–8: Definitions of markedly abnormal biochemistry values

Variable (SI Units)	Markedly Abnormal Definition	
	Low	High
AST	N/A	>5.0 x ULN
Total bilirubin	N/A	>3.0 x ULN
GGT	N/A	>5.0 x ULN
Creatinine (umol/L)	N/A	>3.0 x ULN or >3 x Baseline value ^a
Glucose (mmol/L)	<2.2	>13.9
Calcium (mmol/L)	<1.75	>3.1
Magnesium (mmol/L)	<0.4	>1.23
Potassium (mmol/L)	<3.0	>6.0
Sodium (mmol/L)	<130	>155
Total cholesterol (mmol/L)	N/A	>10.34

ALP=alkaline phosphatase; ALT=alanine aminotransferase; AST=aspartate aminotransferase; GGT=gamma glutamyl transferase; N/A=Not applicable; ULN=upper limit of normal.

^a The markedly abnormal definitions for creatinine are based on the logical OR; if either criterion is met the creatinine value will be designated as abnormal high.

A summary of the number and percentage of subjects with a given Common Terminology Criteria for Adverse Events (CTCAE) grade (0, 1, 2, 3 or 4) based on minimum/maximum on-treatment value in AS0009 (including unscheduled and repeat assessments, but excluding any measurements that occurred prior to the first administration of study medication in AS0009 or more than 140 days after the last administration of study medication), will be presented by laboratory variable and treatment group at completion of AS0008. This summary will be provided only for selected laboratory variables and using central laboratory data only.

Definitions of CTCAE grades are given in [Table 10–9](#) and [Table 10–10](#).

A shift table of the number and percentage of subjects experiencing CTCAE grade 0, 1, 2, 3 or 4 values (as applicable) at AS0009 Laboratory Baseline to minimum/maximum post-AS0009 Laboratory Baseline CTCAE grade will be presented by laboratory variable and treatment group at completion of AS0008. The minimum/maximum post-AS0009 Laboratory Baseline CTCAE grade will include all scheduled and unscheduled on-treatment central laboratory assessments (excluding any measurements that occurred prior to the first administration of study medication in AS0009 or more than 140 days after the last administration of study medication).

Table 10–9: Definitions of CTCAE grade by hematology parameter

Parameter (unit)	Definition	Unit	Grade 1	Grade 2	Grade 3	Grade 4
Hemoglobin	Low	g/L	100-<LLN	80-<100	<80	N/A
Hemoglobin ^a	High	g/L	>0-20 above ULN, or >0-20 above Baseline if Baseline is above ULN	>20-40 above ULN, or >20-40 above Baseline if Baseline is above ULN	>40 above ULN, or >40 above Baseline if Baseline is above ULN	N/A
Platelets	Low	10 ⁹ /L	75-<LLN	50-<75	25-<50	<25
WBC	Low	10 ⁹ /L	3-<LLN	2-<3	1-<2	<1
WBC	High	10 ⁹ /L	N/A	N/A	>100	N/A
Lymphocytes	Low	10 ⁹ /L	0.8-<LLN	0.5-<0.8	0.2-<0.5	<0.2
Lymphocytes	High	10 ⁹ /L	N/A	>4-20	>20	N/A
Neutrophils	Low	10 ⁹ /L	1.5-<LLN	1.0-<1.5	0.5-<1.0	<0.5

LLN=lower limit of normal, ULN=upper limit of normal.

^a The CTCAE grade definitions to be applied are dependent on the Baseline hemoglobin value. If the Baseline value is >ULN then the criteria relative to Baseline are applicable; otherwise the criteria relative to ULN are applicable.

Table 10–10: Definitions of CTCAE grade by biochemistry parameter

Parameter (unit)	Definition	Unit	Grade 1	Grade 2	Grade 3	Grade 4
Creatinine ^a	High	umol/L	>1-1.5 x Baseline or >ULN-1.5 x ULN	>1.5-3.0 x Baseline or >1.5 – 3.0 x ULN	>3.0 x Baseline or >3.0 – 6.0 x ULN	>6.0 x ULN
Sodium	Low	mmol/L	130-<LLN	N/A	120-<130	<120
Sodium	High	mmol/L	>ULN-150	>150-155	>155-160	>160
Potassium ^b	Low	mmol/L	3.0-<LLN	3.0-<LLN	2.5-<3.0	<2.5
Potassium	High	mmol/L	>ULN-5.5	>5.5-6.0	>6.0-7.0	>7.0
Calcium	Low	mmol/L	2.0-<LLN	1.75-<2.0	1.5-<1.75	<1.5
Calcium	High	mmol/L	>ULN-2.9	>2.9-3.1	>3.1-3.4	>3.4
Magnesium	Low	mmol/L	0.5-<LLN	0.4-<0.5	0.3-<0.4	<0.3
Magnesium	High	mmol/L	>ULN-1.23	N/A	>1.23-3.30	>3.30
Cholesterol	High	mmol/L	>ULN-7.75	>7.75-10.34	>10.34-12.92	>12.92

LLN=lower limit of normal, ULN=upper limit of normal.

^a The CTCAE grade definitions for creatinine are based on the logical OR; the highest applicable CTCAE grade should be assigned to a specific creatinine value.

^b Note that subjects who meet the decreased potassium criterion of $3.0 < \text{LLN}$, which is specified as the decreased potassium lab criterion for both CTCAE Grade 1 and Grade 2, will be counted as Grade 2.

The number and percentage of subjects with elevated liver function tests will be presented by treatment group at completion of AS0008 and overall, using on-treatment assessments (excluding any measurements that occurred prior to the first administration of study medication in AS0009 or more than 140 days after the last administration of study medication) from all visits in AS0009 including those at AS0009 Laboratory Baseline, unscheduled, ET and SFU visits. Assessments performed at both central and local laboratories will be included. Each subject will be counted once only. The number and percentage of subjects in the following categories at any time during the study will be presented:

- AST: $>3\times\text{ULN}$, $>5\times\text{ULN}$, $>8\times\text{ULN}$, $>10\times\text{ULN}$, $>20\times\text{ULN}$.
- ALT: $>3\times\text{ULN}$, $>5\times\text{ULN}$, $>8\times\text{ULN}$, $>10\times\text{ULN}$, $>20\times\text{ULN}$.
- AST or ALT: $>3\times\text{ULN}$, $>5\times\text{ULN}$, $>8\times\text{ULN}$, $>10\times\text{ULN}$, $>20\times\text{ULN}$.
- Total bilirubin: $>1.5\times\text{ULN}$, $>2\times\text{ULN}$.
- ALP: $>1.5\times\text{ULN}$.

The number and percentage of subjects who meet Hy's Law criteria ([Section 10.2.3](#)) will be presented by treatment group at completion of AS0008 and overall, using on-treatment assessments (excluding any measurements that occurred prior to the first administration of study medication in AS0009 or more than 140 days after the last administration of study medication) from all visits including those at AS0009 Laboratory Baseline, unscheduled, ET and SFU visits. Hy's Law criteria are displayed below:

- (AST $\geq 3\times\text{ULN}$ or ALT $\geq 3\times\text{ULN}$) and Total Bilirubin $\geq 2\times\text{ULN}$ in the absence of ALP $\geq 2\times\text{ULN}$.

To meet the above criteria, a subject must experience the elevation in total bilirubin and ALT or AST and the absence of ALP elevation at the same visit.

All hematology and biochemistry laboratory data (except CRP) will be listed, including age, sex, race, weight, changes from AS0009 Laboratory Baseline for numeric variables, flags for measurements outside the normal ranges, flags for measurements meeting the criteria for each CTCAE grade ([Table 10–9](#) and [Table 10–10](#)) the relative study day, a flag for whether the test was not done and a flag for whether the subject was fasting.

CRP will be listed separately as described in [Section 8](#).

Values that are below the lower limit of the reference range will be flagged as 'L' (low) and values that are above the upper limit of the reference range will be flagged as 'H' (high) in listings. Values that meet the criteria for each CTCAE grade will be flagged as 'LGrx' or 'HGrx' accordingly.

The markedly abnormal laboratory results will be listed separately.

Any additional laboratory assessments performed during the study will be listed separately.

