2.2.1.3 Other safety variables

Other safety variables are:

- Change from AS0009 Laboratory Baseline (as defined in [Section 3.3](#)) in clinical laboratory variables (hematology and biochemistry, with the exception of high-sensitivity C-reactive protein [CRP]) at each visit (AS0009 Week 24, 36, 48, 60, 72, 84, 96, 108, 120, 132, 144, 156, 168, 180, 192, 204, 208, SFU).
- Change from AS0008 Baseline in vital signs (pulse, temperature and blood pressure) (AS0009 Entry Visit [EV], Week 4, 8, 12, 24, 36, 48, 60, 72, 84, 96, 108, 120, 132, 144, 156, 168, 180, 192, 204, 208, Completion/ET, SFU) and body weight (AS0009 EV, Week 12, 24, 36, 48, 60, 72, 84, 96, 108, 120, 132, 144, 156, 168, 180, 192, 204, 208, SFU).

Note that the change from AS0009 EV variables specified in the protocol will not be reported, since the EV assessment is made after 36 or 48 weeks of bimekizumab treatment and there is unlikely to be any further important change.

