3.3 Definition of Baseline values

The Baseline value defined in the AS0008 database will be used as a Baseline for AS0009, without additional derivation. The change from AS0008 Baseline will be calculated.

Due to a change in laboratory vendor between AS0008 and AS0009, laboratory values (with the exception of CRP) will use the AS0009 Laboratory Baseline, defined as the earliest post-EV value recorded in AS0009 at or prior to AS0009 Week 12 (excluding any local laboratory measurements). Change from AS0009 Laboratory Baseline will be calculated for these parameters. Change from Baseline will not be calculated for local laboratory measurements as there is no Baseline defined for these values.

The CRP values from the two laboratory vendors have been calibrated, so change from AS0008 Baseline will be calculated for CRP.

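### SAP Table 10-10 makes any creatinine above the subject's own baseline at least CTCAE Grade 1, so the Grade 0-to-1 creatinine output is mostly noise

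*SAP*

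**What the plan says.** SAP Section 10.3 plans two CTCAE displays for selected laboratory variables, using central laboratory data. One is a count of subjects by grade of their worst on-treatment value. The other is a shift table, described as "A shift table of the number and percentage of subjects experiencing CTCAE grade 0, 1, 2, 3 or 4 values" "at AS0009 Laboratory Baseline to minimum/maximum post-AS0009 Laboratory Baseline CTCAE grade will be presented". Unscheduled samples count. Samples taken "more than 140 days after the last administration of study medication" do not.

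For creatinine, Table 10-10 sets Grade 1 at ">1-1.5 x Baseline or >ULN-1.5 x ULN". Its footnote states that "The CTCAE grade definitions for creatinine are based on the logical OR" and that the highest applicable grade is assigned. Grades 2 and 3 also carry a baseline limb, starting at 1.5 x and 3.0 x Baseline.

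The reference is one value. SAP Section 3.3 gives the AS0009 Laboratory Baseline as "defined as the earliest post-EV value recorded in AS0009 at or prior to AS0009 Week 12", which will normally be the Week 12 sample. SAP Section 2.2.1.3 lists the scheduled visits for change from that baseline: "AS0009 Week 24, 36, 48, 60, 72, 84, 96, 108, 120, 132, 144, 156, 168, 180, 192, 204, 208, SFU".

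The high-hemoglobin row of Table 10-9 is built differently. There the baseline-relative limits apply only when the subject's baseline is above ULN. Creatinine has no such condition, and nothing elsewhere in the SAP limits its baseline limb.

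**The concern.** The lower bound of the Grade 1 baseline limb is 1 x Baseline, so it has no margin for ordinary within-subject variation. A rise of 1 umol/L, well inside the reference range, meets it. The baseline value cannot exceed itself, so every subject at or below ULN starts at Grade 0. Such a subject stays at Grade 0 only if no later on-treatment sample is higher than that one baseline sample.

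With many later samples, this compares one draw with the maximum of many draws from the same distribution. The Grade 0-to-1 cell then fills up without any renal change and leaves little room for a real change to show. Because the displays are split by treatment group at the end of AS0008, a difference in retention between the groups would also move the Grade 1 rate. In the listings, values within the reference range would carry a high-grade CTCAE flag with no high flag against the reference range.

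**Working it through.** The documents give no expected rate for this output, so there is no figure to reproduce.

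**Inputs from the documents**
- Grade 1 rule: either limb is enough (Table 10-10 and its footnote).
- Baseline: one value (SAP Section 3.3).
- Statistic: worst post-baseline grade, which for creatinine is the grade of the maximum (SAP Section 10.3).
- Scheduled post-baseline samples with full follow-up: Weeks 24 to 204 every 12 weeks, (204 - 24)/12 + 1 = 16, plus Week 208 and the Safety Follow-up (SFU) visit = 18. The SFU visit is due at 20 weeks = 140 days with a window of -3/+7 days (Protocol Section 8). A late SFU sample can therefore fall beyond the 140-day cut-off, leaving 17.

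**Assumed, because the documents do not give them**
- Within-subject CV 4-10%.
- Results either continuous, rounded to 1 umol/L, or rounded to 0.1 mg/dL.
- Population mean 75, SD 13 and ULN 104 umol/L.

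**Exact argument.** Suppose the baseline and k later values are exchangeable (no drug effect, no trend) and untied. Baseline is then the largest of k + 1 values with probability 1/(k + 1), so

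P(at least one later value > Baseline) = k/(k + 1).

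| Post-baseline samples, k | P(some value > Baseline) |
|---|---|
| 18 (full follow-up) | 18/19 = 94.7% |
| 17 (SFU sample too late) | 17/18 = 94.4% |
| 8 (reached Week 108) | 8/9 = 88.9% |
| 7 | 7/8 = 87.5% |
| 3 | 3/4 = 75% |
| 1 | 1/2 = 50% |

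**Simulation, 200,000 subjects, 17 or 18 samples unless stated**
- Rounded to 1 umol/L, CV 4-10%: 92-94% have a value above baseline.
- Same setting, actual upward grade shift (subjects above ULN at baseline are already Grade 1): 91-93% of all subjects, 92-95% of those at Grade 0.
- Correlation between successive visits from 0.3 to 0.9 (18 samples): 94% down to 90%.
- Rounded only to 0.1 mg/dL: 58-84%.
- True change in every subject after baseline, CV 5%, 18 samples: 86% for a 3% fall and 98% for a 3% rise. The no-change figure is 94.7%, so a uniform 3% rise adds only about 3 percentage points.
- Grade 2 or higher by noise: under 0.3% at CV 4-8%, and about 2% at CV 10%.
- Grade 1 defined by ULN alone: chance shift from Grade 0 of about 3-14% (CV 4-10%, continuous or 1 umol/L). This range depends on the assumed mean, SD and ULN.

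**The case against.** The strongest reply is that this is one boundary in a descriptive display. No test or decision uses it, and creatinine is well covered elsewhere: observed values and change from Laboratory Baseline by visit, the markedly abnormal table (above 3 x ULN or 3 x Baseline), and the reference-range flags in the listings. This stands. A reader might infer that the plan cannot show a renal signal. The documents do not support that, because those outputs and Grades 2 to 4 of the same tables still discriminate.

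A reader might also infer that nearly the whole Safety Set will appear as Grade 1. That does not follow. The Safety Set includes everyone with one dose, early dropouts have few samples, and the documents give no dropout distribution. Reporting precision is also unsettled: the SAP uses umol/L, while Protocol Table 17-2 labels creatinine in mg/dL.

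Dependence on the number of visits is not special to creatinine either, since every row of Tables 10-9 and 10-10 uses a minimum or maximum. A ULN-only rule lowers the rate but does not remove that feature.

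Finally, SAP Amendment 2 revised the creatinine grades as part of an update that included alignment with program conventions, and the footnote spells out the OR. The wording therefore looks deliberate. The documents name no CTCAE version and do not reproduce the scale, so they do not show whether the cell departs from it. The point does not need that. Whatever its source, applying this limb to the worst of up to 18 scheduled values against one baseline value gives an uninformative cell.

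**Conclusion.** The point holds for the Grade 0/1 boundary of creatinine and goes no further. As written, a subject with full follow-up and no renal change has an 18/19 = 94.7% chance of a value above baseline if values are exchangeable and untied. The figure is about 91-95% with 1 umol/L rounding and allowance for baselines already above ULN. It falls with fewer visits, coarser reporting, strong serial correlation or a downward drift, and rises with unscheduled samples. Strictly, the result is at least Grade 1, since a value above 1.5 x Baseline is graded higher.

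The affected outputs are the creatinine rows of the grade summary and shift table, and the CTCAE flags in the listings. The primary safety variables, the markedly abnormal table and the change-from-baseline summaries do not use this rule. Grades 2 to 4 are essentially unaffected at the CVs assumed. This should be corrected before the tables are produced, but it does not threaten the study's safety conclusions.

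**What to change.** In SAP Table 10-10, define creatinine Grade 1 as above ULN up to 1.5 x ULN. Keep the baseline limbs for Grades 2 and 3, and footnote the change. Grade 0 is then at or below ULN and no more than 1.5 x Baseline.

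An alternative is to let the Grade 1 baseline limb apply only when baseline is above ULN, as for high hemoglobin in Table 10-9. If that limb then replaces the ULN limb, as it does for hemoglobin, those few subjects would start at Grade 0 and face the same noise. The ULN-only cell is simpler.

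If the program's grade wording must be kept, leave the definition alone. Split Grade 1 in the summary and shift tables into values above ULN and values above baseline only but within ULN.

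The cost is one table cell and a footnote, or one extra row. No new data are needed. The downside is a small departure from the program's grade wording, which the split avoids.
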